7.2 NULL AND ALTERNATIVE HYPOTHESES

Two safety hypotheses (110mg Dabigatran Etexilate (DE-DAT) vs. warfarin-TAT and 150mg DE-DAT vs. warfarin-TAT) will be tested:

1. 110mg DE-DAT is non-inferior to warfarin-TAT with respect to MBE/CRNMBE over the duration of the trial
2. 150mg DE-DAT is non-inferior to warfarin-TAT with respect to MBE/CRNMBE over the duration of the trial.

To control the Type I error rate at a one-sided 0.025 level, a hierarchical procedure for multiple testing will be used to test the above hypotheses. Additional testing for safety and efficacy endpoints will also be included in this hierarchical procedure. The following hierarchical procedure will be applied:

Step 1 – Non-inferiority of 110mg DE-DAT to warfarin-TAT in MBE/CRNMBE is met at the one-sided 0.025 level of significance

Step 2 – Non-inferiority of 150mg DE-DAT to warfarin-TAT in MBE/CRNMBE is met at the one-sided 0.025 level of significance

Step 3 – Non inferiority of 150mg DE-DAT and 110mg DE-DAT combined to warfarin-TAT in DTE and unplanned revascularisation by PCI/CABG is met at the one-sided 0.025 level of significance

Proprietary confidential information.

© 2016 Boehringer Ingelheim International GmbH or one or more of its affiliated companies. All rights reserved.

This document may not - in full or in part - be passed on, reproduced, published or otherwise used without prior written permission.

Step 4 – Superiority of 110mg DE-DAT to warfarin-TAT in MBE/CRNMBE is met at the one-sided 0.025 level of significance

Step 5 – Non inferiority of 150mg DE-DAT and 110mg DE-DAT combined to warfarin-TAT in DTE is met at the one-sided 0.025 level of significance

Step 6 – Superiority of 150mg DE-DAT to warfarin-TAT in MBE/CRNMBE is met at the one-sided 0.025 level of significance

If any of the steps above fail to meet statistical significance, the testing procedure will stop at that step and subsequent tests will not be performed.

The Non-Inferiority (NI) margin used for MBE/CRNMBE will be 1.38 (on the relative HR scale). See [Section 7.6](#) for a clinical justification of this margin. The upper bound of the Wald confidence interval (CI) of the HR of DE-DAT vs. warfarin-TAT (one-sided 97.5%) will be compared to this NI margin for the NI testing.

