7.6 DETERMINATION OF SAMPLE SIZE

This is an event-driven trial where it is assumed that the first patient recruited into the study will be followed up for a maximum of approximately 30 months and the last patient recruited into the trial will be followed up for a minimum of 6 months. It is assumed that patient accrual will be approximately uniform over the 24 month recruiting period.

The proportion of patients with at least one MBE/CRNMBE at one year is estimated to be 14% based on current blinded trial data.

A relative NI margin for the original co-primary endpoint (DTE) was chosen in analogy to recent SPAF trials with primary endpoints of stroke/SE, where 1.38 was used by the FDA for ximelagatran, apixaban, rivaroxaban and dabigatran to preserve at least 50% of the relative reduction (on the log scale) in the risk associated with warfarin in six previous (historical), randomised, controlled trials. See publication by Jackson K, Gersh BJ, Stockbridge N, et al. [[R08-2662](#)]. The same NI margin has been applied to MBE/CRNMBE as it was considered the most clinically relevant available reference in the absence of any other type of data.

The overall sample size is driven by the non-inferiority comparison of MBE/CRNMBE between 110mg DE-DAT or 150mg DE-DAT and warfarin-TAT. With $\alpha=0.025$ (one-sided) and 14% of patients with at least one event at one year, 334 patients with at least one MBE/CRNMBE in each pair of treatment groups (i.e. 167 patients with MBE/CRNMBE per treatment group) are required to achieve 83.6% power for this endpoint, yielding a final sample size estimated at 834 patients in each treatment group (i.e. 2502 randomised patients in total). Therefore approximately 500 patients with at least one MBE/CRNMBE are required in total across the three treatment groups.

Proprietary confidential information.

© 2016 Boehringer Ingelheim International GmbH or one or more of its affiliated companies. All rights reserved.

This document may not - in full or in part - be passed on, reproduced, published or otherwise used without prior written permission.

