D3.1	Mandatory medication not taken per protocol (ASA)	ASA not taken for the first month for warfarin patients with a BMS or for the first three months for patients with a DES as indicated on the Trial Medication Compliance eCRF page (exclude if at least one visit is ticked "No").	PPS, but only from start of non-compliance onwards
D3.2	Mandatory medication not taken per protocol (clopidogrel/ticagrelor)	Clopidogrel/ticagrelor non-compliance during the first 12 months of treatment as indicated on the Trial Medication Compliance eCRF page (exclude if at least one visit is ticked "No").	PPS, but only from start of non-compliance onwards
G	Trial Specific Protocol Violations		
G1	Patient not withdrawn from treatment if CrCl drops to <30mL/min at two different occasions during the trial	As per study protocol, this only applies to patients randomised to dabigatran etexilate.	PPS

KEY: PPS – Per Protocol Set

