6.3 PATIENT SETS ANALYSED

The following analysis sets will be defined for this trial:

- **SCR – Screened Set**
All patients who signed informed consent and completed at least some screening procedures.
- **FAS – Full Analysis Set**
All consenting patients randomised will be analysed in the treatment group to which they are randomised regardless of whether they took study medication. The start date of the observation period for this analysis set is the date of randomisation. This follows the intent-to-treat principle. All patient listings will be based on the FAS except where specified otherwise. Refer to the technical TSAP for more detail.
- **TS – Treated Set**
The set of patients who receive at least one dose of study medication will be analysed according to the treatment they have received. The start date of the observation period for this analysis set is the date of first intake of trial medication.

- PPS – Per-Protocol Set
Patients will be included in the PPS, if they are already included in the TS and if they adhere to the trial protocol without any IPVs. IPVs are defined in [Section 6.2](#).

For rules on censoring, refer to [Section 7.4](#).

The final decision as to whether a patient is included in or excluded from each analysis set will be taken before database lock in a blinded manner, where possible and will be documented in the minutes of the RPM or Database Lock Meeting (DBLM). Some decisions may need to be taken after DBL (e.g. treatment switching). If the number of patients excluded from the PPS is small (<10% of the TS), then analyses on this set may not be conducted. This decision will also be documented in the minutes of the RPM or DBLM.

The following table identifies which patient set is used for which category of endpoints.

[figure not shown]
Table 6.3: 1 Patient sets analysed

[figure not shown]
Class of endpoint	Patient set		
	FAS*	TS	PPS#
Primary endpoint (see Section 5.1)	X	X	X
Secondary endpoints (see Section 5.2.2)	X	X	
Further endpoints (see Section 5.3)	X	X	
Safety endpoints other than the primary endpoint (see Section 7.8)	X	X	
Other safety endpoints (see Section 7.8.5)	X	X	
Demographic/baseline endpoints (see Section 7.1)	X		X

[figure not shown]
Note that the number of patients with available data for an endpoint may differ. For details, see [Section 6.6](#).

* The FAS will be the main analysis set for the summary of clinical outcome event data. Other analysis sets will be used for sensitivity purposes.

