For patients with DTEs and other OEs that include death (see [Section 7.5.2](#)), the date of death will not be used for censoring purposes, but instead will count as an event. In general, if the date last seen coincides with the date of any outcome event reported, this outcome event will be counted for the primary analysis.

These censoring rules determine the "time at risk" for counting of events for the primary analysis.

The robustness of the primary analysis will be assessed by an on-treatment analysis of the TS and the PPS. The same censoring rules as defined above will be used. However, for patients who already had their EOT visit (i.e. those who stopped treatment prematurely), they will be censored at the date of their last trial medication intake plus 6 days. It will also analyse patients by the actual treatment taken.

The censoring rules defined for the on-treatment analysis determine the "time at risk" for counting of events for the on-treatment analysis, i.e. the on-treatment analysis will only count events that occur while a patient is taking study medication (+ REP of 6 days, if study

medication is stopped prematurely before study end). The date of first intake of study medication will be used as the start of the analysis period in this analysis instead of the date of randomisation. Intermittent off-treatment periods will be ignored in cases of any temporary interruptions in study medication.

These analyses will be based on the TS and the on-treatment period.

The proportional hazards assumption will be investigated for the primary analysis only. The following techniques will be used:

- Plotting log (-log (survival function)) against the log of time by treatment group. Parallel curves are consistent with the proportional hazards assumption.

- Adding time-dependent variables to the Cox model
For each variable in the model an interaction term is derived by multiplying by the log of time and adding to the model. Non-significance at the 5% level is consistent with the proportional hazards assumption.

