A summary of adjudication will be presented showing the number of investigator-reported OEs along with whether they were positively or negatively adjudicated or whether they were non-assessable. Further analyses will be performed on investigator reported events (i.e. those that are positively and negatively adjudicated). A sensitivity analysis will be performed that includes any non-assessable events into the positively adjudicated MBE/CRNMBE category.

Two safety hypotheses (110mg DE-DAT vs. warfarin-TAT and 150mg DE-DAT vs. warfarin-TAT) will be tested:

1. 110mg DE-DAT is non-inferior to warfarin-TAT with respect to MBE/CRNMBE over the duration of the trial

2. 150mg DE-DAT is non-inferior to warfarin-TAT with respect to MBE/CRNMBE over the duration of the trial.

To control the Type I error rate at a one-sided 0.025 level, a hierarchical procedure for multiple testing will be used to test the above hypotheses. Additional testing for safety and efficacy endpoints will also be included in this hierarchical procedure. The following hierarchical procedure will be applied:

Step 1 – Non-inferiority of 110mg DE-DAT to warfarin-TAT in MBE/CRNMBE is met at the one-sided 0.025 level of significance

Step 2 – Non-inferiority of 150mg DE-DAT to warfarin-TAT in MBE/CRNMBE is met at the one-sided 0.025 level of significance

Step 3 – Non inferiority of 150mg DE-DAT and 110mg DE-DAT combined to warfarin-TAT in DTE and unplanned revascularisation by PCI/CABG is met at the one-sided 0.025 level of significance

Step 4 – Superiority of 110mg DE-DAT to warfarin-TAT in MBE/CRNMBE is met at the one-sided 0.025 level of significance

Step 5 – Non inferiority of 150mg DE-DAT and 110mg DE-DAT combined to warfarin-TAT in DTE is met at the one-sided 0.025 level of significance

Step 6 – Superiority of 150mg DE-DAT to warfarin-TAT in MBE/CRNMBE is met at the one-sided 0.025 level of significance

If any of the steps above fail to meet statistical significance, the testing procedure will stop at that step and subsequent tests will not be performed.

The Non-Inferiority (NI) margin used will be 1.38 (on the relative hazard ratio (HR) scale). See Section 7.6 of the CTP for a clinical justification of this margin. The upper bound of the Wald confidence interval (CI) of the HR of DE-DAT vs. warfarin-TAT (one-sided 97.5%) will be compared to this NI margin for the NI testing.

Kaplan-Meier survival figures will be presented by treatment group/strata and by treatment group.

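### The rule for skipping the per-protocol sensitivity analysis uses a pooled, incompletely defined 10% count and should be dropped (minor)

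*SAP*

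**What the plan says.** SAP 6.3 defines the Per-Protocol Set (PPS) as treated patients who have no important protocol violation (IPV). It then adds a condition, repeated as a footnote to Table 6.3:1: "If the number of patients excluded from the PPS is small (<10% of the TS), then analyses on this set may not be conducted". The Treated Set (TS) is everyone who took at least one dose, in any arm.

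Table 6.3:1 schedules the PPS for the primary endpoint, and SAP 7.4 states: "The robustness of the primary analysis will be assessed by an on-treatment analysis of the TS and the PPS".

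In SAP Table 6.2:1 most violations remove the patient from the PPS altogether. Codes C3 (study-drug compliance or INR control), D3.1 (aspirin) and D3.2 (clopidogrel or ticagrelor) are different: "PPS, but only from start of non-compliance onwards".

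On timing, SAP 6.3 wants set membership settled before database lock where possible, but adds: "Some decisions may need to be taken after DBL (e.g. treatment switching". SAP 6.2 likewise says that some programmed violations can be found only after lock. The decision to skip the PPS analysis is to be recorded in the minutes of the report planning or database lock meeting.

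The full analysis set (FAS) is the main set, and the other sets are for sensitivity.

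**The concern.** In a non-inferiority comparison, non-adherence and ineligible patients can pull the FAS hazard ratio towards 1, which helps the claim. A per-protocol analysis is informative when exclusions are unequal between arms or related to bleeding. The 10% rule measures neither.

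- **Pooled over arms.** Each primary test compares one dabigatran dose with warfarin, but the count covers all three arms. Violation rules differ by arm. D3.1 and the INR part of C3 apply to warfarin; G1 and item 4 of D2.1 apply to dabigatran. The overlap limits in D2.1 differ by arm, and only warfarin patients have an early aspirin allowance.
- **Unclear numerator.** By the 6.3 definition, C3, D3.1 and D3.2 patients are out and would be counted. By the last column of Table 6.2:1 they stay in until non-compliance starts and might not be. The SAP does not settle this.
- **Timing.** The skip decision belongs to meetings at or before lock, when the count may still be incomplete.

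At stake is the only planned analysis of the primary endpoint that removes eligibility, prohibited-medication and on-treatment compliance violators.

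**Working it through.** **Inputs.** SAP 7.4: "To control the Type I error rate at a one-sided 0.025 level", so z = 1.96. Protocol 7.2: "The Non-Inferiority (NI) margin used for MBE/CRNMBE will be 1.38 (on the relative HR scale". Protocol 7.6: "334 patients with at least one MBE/CRNMBE in each pair of treatment groups" (167 per arm), with 834 patients per arm and 2502 in total; these events "are required to achieve 83.6% power for this endpoint".

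**Assumptions not in the documents.** All 2502 are treated; the true HR is 1 for the power check; exclusions remove whole patients; the event rates among excluded patients are as stated below.

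**1. The plan's own figure.** Power = Φ(ln 1.38 × √334 / 2 − 1.96) = Φ(2.943 − 1.960) = Φ(0.983) = 83.7%, against 83.6% stated. The design is reproduced.

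**2. Starting point.** With 167 v 167 events and HR 1.00, the upper bound is exp(1.96 × 2/√334) = 1.239. The observed HR must be below 1.38/1.239 = 1.114.

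**3. What the rule allows.** 10% × 2502 = 250.2, so up to 250 patients. That is 250/1668 = 15.0% of a two-arm comparison, or 250/834 = 30.0% of one arm.

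**4. Balanced exclusions.** Remove 83 from each of the two arms at the arm's own rate of about 20%. Each arm keeps 167 − 16.6 = 150.4 events, HR stays 1.00, and the bound is exp(1.96 × √(2/150.4)) = 1.254.

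**5. All 250 from warfarin.** Let r be the event rate in excluded patients relative to retained ones. PPS HR = 0.7 + 0.3r; retained warfarin events = 167 × 0.7/(0.7 + 0.3r); bound = HR × exp(1.96 × √(1/167 + 1/retained events)).

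| r | PPS HR | Retained events | Bound |
|---|---|---|---|
| 1.25 | 1.08 | 108.8 | 1.37 |
| 1.5 | 1.15 | 101.7 | 1.47 |
| 2.0 | 1.30 | 90.0 | 1.68 |

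The last two exceed 1.38.

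**6. Exclusions from one dabigatran arm only.** HR = ln(1 − e₁/n₁)/ln(1 − e₂/n₂), bound = HR × exp(1.96 × √(1/e₁ + 1/e₂)). For 76 removed, none of whom bled: ln(1 − 167/758)/ln(1 − 167/834) = 1.114, times 1.239 = 1.38. The smallest number removed that lifts the bound to 1.38, with its share of the TS, is:

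| Share of removed who bled | From HR 1.00 (167 v 167) | From HR 0.90 (159 v 175) |
|---|---|---|
| 0% | 76 (3.0%) | 145 (5.8%) |
| 5% | 97 (3.9%) | 183 (7.3%) |
| 10% | 134 (5.4%) | 247 (9.9%) |
| 15% | 217 (8.7%) | 381 (15.2%, above the rule) |
| 20% | never | never |

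From HR 0.80 (150 v 184) it takes 215 (8.6%) at 0%, and 267 (10.7%, above the rule) at 5%.

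**7. Would a 10% limit per arm suffice?** It would cap removals at 83 per arm. Removing 83 from the dabigatran arm alone gives a bound of 1.320 if 10% had bled, 1.357 if 5% had, and 1.395 if none had. It prevents most reversals, but not all.

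**The case against.** The PPS is a sensitivity analysis. Non-inferiority is tested on the FAS, and Protocol 7.3.1 does not plan a PPS analysis at all; the SAP added it. A reader might infer that a skipped PPS could hide a result that overturns non-inferiority. The documents do not support that: the PPS could disagree with the FAS, but it has no formal power to reverse it. This stands.

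Dilution is also partly handled elsewhere. The on-treatment TS analysis in SAP 7.4 is not subject to the 10% rule. It censors early discontinuers six days after last intake and analyses actual treatment. SAP section 4 drops the switch-censoring analysis because it would nearly duplicate this one. This also stands, but violators who stay on treatment are kept in that analysis: ineligible patients, users of prohibited drugs and poor compliers.

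A reader might further infer that the rule certainly misses time-limited violators. That is only one reading. The 6.3 definition points to counting them; the last column of Table 6.2:1 points the other way. It is an ambiguity. It also weakens the warfarin example, because the warfarin-only codes (D3.1, the INR part of C3) are the time-limited ones and may not supply counted exclusions. The dabigatran calculation in step 6 does not depend on those codes.

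The apparent clash between SAP 7.4 and 6.3 is mild, since the table footnote states the condition and the wording is permissive. SAP 6.3 also allows some set decisions after lock. SAP section 7 promises a table of violations leading to PPS exclusion, though it does not say that the table will be by arm.

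**Conclusion.** The concern holds as a minor weakness in a sensitivity analysis. The skip rule does not look at balance between arms, leaves the status of C3, D3.1 and D3.2 patients open, and may be applied before the count is final. Below its ceiling of 250 patients, the PPS bound could pass 1.38 while the FAS passes. From HR 1.00, 76 to 217 exclusions from one dabigatran arm would do it if 0% to 15% of them had bled; 250 from warfarin would do it at 1.5 times the retained rate, but not at 1.25 times.

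These are possibilities, not forecasts. They need exclusions that are unbalanced by arm, related to outcome, or both, and they become harder to reach as the FAS hazard ratio falls below 1. The sizes rest on all patients being treated, planned arm sizes of 834, equal or near-equal event splits, and assumed bleeding rates among those excluded. Actual numbers will differ, especially for the 150 mg comparison, which leaves out elderly warfarin patients from outside the USA.

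**What to change.** Delete the 10% sentence in SAP 6.3 and the matching footnote to Table 6.3:1. State that the PPS analysis of the primary endpoint will be run for both dose comparisons, whatever the number excluded, once all IPVs have been identified, including those found after lock. Align the PPS definition in 6.3 with the last column of Table 6.2:1, so that it is clear that C3, D3.1 and D3.2 censor follow-up rather than remove the patient, if that is the intention. Report full exclusions and time-censored patients separately by arm.

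A 10% limit per arm would be a weaker alternative, because step 7 shows that it can still permit a discordant result to be skipped.

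The cost is small: one further model per dose comparison, on a set that the SAP already defines and schedules, plus one by-arm table. Neither the primary test nor the hierarchy changes.

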6.5 POOLING OF CENTRES

This section is not applicable because centre/region is not included in the statistical model. However, consistency of treatment effects across regional subgroups will be investigated (see [Section 6.4](#)).

6.6 HANDLING OF MISSING DATA AND OUTLIERS

A major goal of the trial is to obtain virtually complete follow-up of vital status and full collection of outcome event data. As mentioned in [Section 7.4](#), all patients lost to follow-up will be treated as censored at the time of last known vital status. This section contains details of how censoring will be performed for patients who do not experience outcome events.

The CTR will contain a summary of the number and percentage of patients with (and without) complete follow-up of vital status in each treatment group.

Due to the nature of the adjudication process, it may not be possible to classify bleeds under every bleed definition (i.e. TIMI and BARC). In these instances, the bleed classification will be left missing and no imputation will be attempted. Classification of bleeds under the ISTH definitions should not be left missing by the IAC.

In general, missing investigator INR ranges will be imputed with the standard guideline range for this patient population which is 2-3. The exception to this is for patients in Japan who are ≥ 70 years old. The guideline range for these patients is 2 – 2.6.

Missing or incomplete AE dates/times are imputed according to BI standards (see “Handling of missing and incomplete AE dates”) [[1](#)]. The same philosophy will be applied to missing or incomplete outcome event and concomitant medication dates/times. Incomplete dates of temporary study medication discontinuation and restart will be imputed. See the TSAP Analysis Dataset (ADS) Plan for further details. Other special handling for missing/incomplete dates/times will be documented in the RPM.

Other missing data will not be imputed. If date of birth/age is missing for a patient, they will not be included in models that use age group as a stratifying factor.

